8.5 DOSE-LIMITING TOXICITIES

Dosing will stop if a dose-limiting toxicity is encountered in a dosing cohort. Events that constitute a dose-limiting toxicity will be defined in the DSMB charter. Dose-limiting toxicities will include:

- Severe or persistent ocular inflammation.
- Other significant ocular toxicity (eg, large retinal detachment, evidence of direct toxicity).
- Other systemic toxicities (eg, acute allergic reaction).
- Any safety issue that has been identified that adversely changes the benefit/risk balance to study participants.

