9.3.11.4 Fundoscopy

Dilated funduscopic examination will be performed according to the investigator's standard practice. Investigators will specifically document the presence or absence of retinal detachment, retinal tears or holes, subretinal hemorrhage, exudation, fluid or fibrosis. Additional observations will also be documented.

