13.4.2 Ophthalmological Safety Endpoints

Changes in other safety endpoints will be summarized at each visit; in addition, where appropriate, individual profile plots and mean plot of changes in the variable against time will be presented. The primary time points will be considered the 48-week (12-month) visit; the individual change at this time point only will be plotted against dose received.

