5.0 ENDPOINTS

5.1 Primary Endpoints

The primary objective of this study is evaluation of safety and tolerability of ascending doses of UshStat in patients with Usher syndrome type 1B. Safety and tolerability of the IMP will be evaluated using the following endpoints:

- The incidence of AEs over a 12-month period following a single intraocular dose of UshStat.
- Clinically important changes from baseline (Day -28) in the following safety assessments:
 - Best-corrected visual acuity (BCVA)
 - Slit-lamp examination
 - Indirect ophthalmoscopy
 - Fundus photography
 - Intraocular pressure (IOP)
 - Ocular coherence tomography (OCT)
 - Laboratory parameters
 - Vital signs
 - Concomitant medications
 - Physical examinations

For all primary endpoints with repeated measures, the primary time point will be considered the Week 48 (12-month) visit unless otherwise specified. BCVA and perimetry measurements are subject to broad intra-individual variability therefore the baseline value used for these measures will be an average of all the values obtained during the screening period.

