7.3 Primary Endpoint

The primary endpoint is composed of several endpoints related to safety, each of which will be presented at the patient and eye level (refer to [Sections 8](#) and [9](#)). Primary analysis for these endpoints, except adverse events, will compare change from Day -28 to Week 48. Graphical presentation of cohort summaries will also be presented as described, and clinically important changes from Baseline (Day -28) to Week 48 will be indicated and summarized.

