7.4.4 Supplementary Reading Center Data

Fundus photography photomontage, fundus autofluorescence (FAF), and microperimetry data will all be analyzed separately by Translational Clinical Trials Center (TCTC) at Casey Eye Institute, the Central Reading Center at the end of the study. These exploratory measures will not be summarized for DSMB meetings.

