9.1 Baseline Characteristics

DEMOGRAPHY												
Patient ID	Cohort	Date of birth	Age	Gender	Race	Ethnicity	Study Eye	Screening Date	Surgery Date	Termination Date	Mutation	
COMMENTS:												

OCULAR MEDICAL HISTORY		
Condition	Study Eye	Diagnosis Date
COMMENTS:		

MEDICAL HISTORY		
Disease/Disorder	Date of Diagnosis	Ongoing
COMMENTS:		

PRIMARY ENDPOINTS (ADVERSE EVENTS)											
AE Description		Start Date (Study Day)	End Date Ongoing	Outcome	Severity	AESI	SAE	Related to Surgery	Related to Investigation Medicinal Product	System Organ Class	Preferred Term
COMMENTS:											

STUDY EYE EXAMINATION (ABNORMALITIES)								
Visit	Macular Edema	Abnormal Optic Nerve	Retinal Detachment	Intraretinal Hemorrhage	Subretinal Hemorrhage	Subretinal Fibrosis	Other	Specify Other
COMMENTS:								

IMMUNOLOGY					
Visit	ELISA Assay Result-Baseline	ELISA Assay Result-Post Admin	Positive/Negative ELISA Response	Western Blot Required	Positive/Negative Western Blot Result

¹The SC1 BCVA is not presented in the table because the SC2 BCVA is an average of the SC1 and SC2 BCVA values.

OCT														
	Central Macular Thickness		Macular Volume		Evidence of Treatment Efficacy		Increase in Cystoid Macular Edema		Unfavorable Change in Subretinal Fluid		Reported AE			
Visit	Study	Fellow	Study	Fellow	Study	Fellow	Study	Fellow	Study	Fellow	Study	Fellow	Study	OCT Data
COMMENTS:														

PERIMETRY														
	Static (GATE) Perimetry			Kinetic (SKP) Perimetry										
	Volume of Full Field Hill of Vision (Decibel Steradians)	111 pt grid-Volume of Full Field Hill of Vision (Decibel Steradians)		Study	Fellow	Study	Fellow	Study	Fellow	Study	Fellow	Study	Fellow	VI4E Isopter Area (Squared Degrees)
Visit	Study	Fellow	Study	Fellow	Study	Fellow	Study	Fellow	Study	Fellow	Study	Fellow	Study	Fellow
COMMENTS:														

FULL-FIELD ERG RESPONSE														
	Light adapted 3.0 flicker ERG	Light adapted 3.0 ERG a-wave	Light adapted 3.0 ERG b-wave	Dark adapted 3.0 ERG a-wave	Dark adapted 3.0 ERG b-wave	Dark adapted 0.01 ERG b-wave								
Visit	Amp	Imp Time	Amp	Imp Time	Amp	Imp Time	Amp	Imp Time	Amp	Imp Time	Amp	Imp Time	Comments	
COMMENTS:														

MEAN PEAK AMPLITUDES AND LATENCIES AT BASELINE (mfERG)														
	Amplitude (nV/deg ²) - max+min Latency (ms)													
	Ring 1		Ring 2		Ring 3		Ring 4		Ring 5		Ring 6		Comments	
Visit	Study	Fellow	Study	Fellow	Study	Fellow	Study	Fellow	Study	Fellow	Study	Fellow	Study	Fellow

[figure not shown]

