The purpose of this memorandum is to document that the Table of Contents for the final analysis for TDU13600 will differ from the Table of Contents in the currently approved version 2 of the SAP, dated 22JUL2016. The format of the tables will be the same as those in the SAP, except that the adverse event tables will be updated to the format used for the 23MAY2018 DSMB Report for SAR422459. The TOC and the adverse event table shells to be used for the final TLFs are included below.

Coordinating Center

Statistician Signature:

[figure not shown]
Date: 30AUG2019

Sponsor Statistician

Signature:

[figure not shown]
Date: 04SEP2019

Coordinating Center

Director Signature:

Date: 24SEP2019

TOC FOR ALL TLFs FOR TDU13600

- [Table 1A](#): Screening and Surgery Dates and Visit Completion by Cohort
- [Figure 1B](#): Patient Flow Diagram
- [Table 1C](#): Study Follow-up Completion and Withdrawal (including deaths)
- [Table 2A](#): Demographics Summary by Cohort
- [Listing 2B](#): Detailed Demographic Listing by Cohort
- [Listing 2C](#): General Medical History by Patient
- Listing 2D: Study Eye Ocular History by Patient
- Listing 2E: Fellow Eye Ocular History by Patient
- [Table 2F](#): Baseline Physical Examination Parameters by Cohort
- Table 2G: Reproductive Status by Patient
- Listing 2H: Detailed Surgery Listing by Patient
- Table 3A: Number and Percentage of Patients Experiencing TEAEs or No Events by Type of Event and Cohort
- Table 3B: Number of Patients Experiencing TEAEs by MedDRA SOC, HLGT, HLT, PT, and Cohort
- Table 3C: Number of Patients with TEAEs of Special Interest by MedDRA SOC, HLGT, HLT, PT, and Cohort
- Table 3D: Number of Patients with SAEs by MedDRA SOC, HLGT, HLT, PT, and Cohort
- Table 3E: Number of Patients Experiencing Inflammatory TEAEs by MedDRA SOC, HLGT, HLT, PT, and Cohort
- Table 3F: Number of Patients with TEAEs Related to IMP by MedDRA SOC, HLGT, HLT, PT, and Cohort
- Table 3G: Number of Patients with TEAEs Related to Procedure by MedDRA SOC, HLGT, HLT, PT, and Cohort
- [Table 3H](#): Listing of Adverse Events Prior to Treatment by Patient and Cohort
- [Table 3I](#): Listing of TEAEs by Patient and Cohort
- [Table 3J](#): Listing of Treatment Emergent Adverse Events of Special Interest by Patient and Cohort
- Table 3K: Listing of Treatment Emergent Serious Adverse Events by Patient and Cohort
- [Listing 3L](#): Ophthalmic Outcome Listing for Study Eye and Fellow Eye by Patient and Visit

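### Structural fundus findings belong to the primary safety endpoint, but the default Day -28 versus Week 48 contrast scores a resolved detachment or hemorrhage as no change, and no final output counts these findings by cohort

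*SAP*

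**What the plan says.** SAP 5.1, like Protocol 6.1, puts ten assessments under the primary safety endpoint, introduced as "Clinically important changes from baseline (Day -28) in the following safety assessments". Indirect ophthalmoscopy and fundus photography are two of them.

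SAP 7.3 then sets one rule for all components: "Primary analysis for these endpoints, except adverse events, will compare change from Day -28 to Week 48". Subsections 7.3.1 to 7.3.9 cover adverse events, BCVA, ocular inflammation, IOP, OCT, laboratory values, vital signs, concomitant medications and physical examination. Ophthalmoscopy enters only through the vitreous cell, haze and macular edema scores in 7.3.3. Fundus photography does not enter at all. SAP 7.4.4 sends the photomontage, autofluorescence and microperimetry to the reading center for separate analysis and adds: "These exploratory measures will not be summarized for DSMB meetings".

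On data collection, Protocol 9.3.11.4 is specific: "Investigators will specifically document the presence or absence of retinal detachment, retinal tears or holes, subretinal hemorrhage, exudation, fluid or fibrosis". On reporting, Protocol 13.4.2 states: "Changes in other safety endpoints will be summarized at each visit".

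The memo of 30 August 2019 attached to the SAP replaces the list of outputs with one headed "TOC FOR ALL TLFs FOR TDU13600".

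**The concern.** The injection raises a subretinal bleb, and Protocol 8.5 gives a large retinal detachment as an example of a dose-limiting toxicity. Complications of this kind can appear and resolve within 48 weeks. A contrast that looks only at Day -28 and Week 48 cannot register such an event.

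If no table or listing covers these findings either, the examination data reach the cohort-level safety conclusion only where someone also reported an adverse event. Naming the examinations as primary components gives a check on adverse-event reporting that does not depend on that reporting. That check would be lost at cohort level.

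**Working it through.** There is no design figure to reproduce: SAP 6.1 states that no formal sample size calculation was made. The check sets the sections side by side and adds a short illustration.

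**1. Is there a specific rule?** SAP 7.3.3 flags a change of two steps or more in inflammation grade at any point from Day -28 to Week 48. SAP 7.3.4 counts IOP at or above 25, 30 and 35 mmHg at any point in the same period (the memo's title for the elevated-IOP table names Week 48, but 7.3.4 itself is an any-point rule). SAP 7.3.9 defines a clinically significant change for physical examination. For detachment, tears or holes, hemorrhage, exudation and fibrosis, and for fundus photographs, there is neither an any-point rule nor a definition of change. The photomontage sent out under 7.4.4 is taken only at screening and Week 48 (Protocol Section 2, footnote b), so the other follow-up photographs are outside it. The default in 7.3 is what remains.

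**2. How much of the schedule does the default use?** Post-surgery assessments counted from Protocol Section 2:

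| | Fundoscopy | Fundus photography, including the intra-operative photograph |
|---|---|---|
| Cohorts 1-3a | 8 (Day 1; Weeks 1, 2, 4, 12, 24, 36, 48) | 7 (Day 0; Day 1; Weeks 2, 4, 24, 36, 48) |
| Cohorts 3b-5 | 7 (no Week 36) | 6 (no Week 36) |

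The contrast uses one of each. A finding absent at Day -28, present in between and absent at Week 48 gives a change of zero.

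**3. What outputs exist?**
- *SAP Section 8:* no shell for structural fundoscopy or fundus photographs. Table 3L carries IOP, BCVA, anterior cells and flare, vitreous cells and haze, and macular edema. Table 3U does list unfavorable change in subretinal fluid on OCT for both eyes.
- *Memo list:* keeps the OCT listing as 3EE and has no entry for the other findings. Listing 2H covers surgery and might show a tear made during the procedure, but no shell is given. The concomitant-medication listing promised in SAP 7.3.8 is also absent.
- *SAP Section 9 profiles:* a by-visit study-eye table with columns for detachment, intraretinal and subretinal hemorrhage, fibrosis and other; and a by-visit photograph table with hemorrhage and detachment for both eyes. Neither is summarized by cohort, and the memo's list does not mention the profiles.

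**4. Size for one patient.** With the memo's N=3 per cohort and N=9 overall, one detachment seen at Week 2 and resolved by Week 24 is 1/3 = 33% and 1/9 = 11% on an any-visit count. On the contrast it is 0/3 and 0/9.

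**5. Range under assumed rates.** Let p be the share of patients with a finding and r the share of those findings resolved by Week 48. The documents give neither, so both are assumptions. The chance that at least one of n patients is flagged is 1 - (1 - p)^n for an any-visit count and 1 - (1 - p(1 - r))^n for Week 48 alone.

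| n | p | Any visit | Week 48, r=0.5 | r=0.8 | r=1 |
|---|---|---|---|---|---|
| 3 | 0.20 | 0.49 | 0.27 | 0.12 | 0 |
| 9 | 0.10 | 0.61 | 0.37 | 0.17 | 0 |
| 9 | 0.20 | 0.87 | 0.61 | 0.31 | 0 |

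For example, 1 - 0.9^9 = 0.61 and 1 - 0.98^9 = 0.17.

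**The case against.** The strongest reply is that little is actually hidden. SAP 7.0 makes patient profiles part of the analysis and says safety results from every visit will be shown. The profile shells cover both components. Adverse-event incidence is itself primary and is exempt from the Week 48 contrast, so a detachment reported after dosing is counted in the TEAE tables. An adverse event needing surgery to prevent permanent sight loss is also an ocular AESI (Protocol 11.5), with 24-hour reporting. In those cases the cohort tables would show the same 1/3 and 1/9.

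Most of this stands, and it rules out three stronger readings that a reader might infer:
- *These components have no output at all.* Not supported: the Section 9 shells exist. The memo omits them from its list but does not withdraw them, so their status is unclear.
- *A resolved event disappears from the primary endpoint.* Not supported: it is lost from the examination-based contrast, not from adverse-event incidence.
- *Dose-escalation decisions rest on this contrast.* Not supported: fundoscopy data are in the DSMB's minimum package (Protocol 13.7, SAP 6.5), and the exclusion in SAP 7.4.4 does not name fundoscopy.

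Nor are these the only components without a titled subsection. Slit-lamp examination has none either, and is covered through its inflammation grades.

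What the reply does not supply is a defined comparison or a cohort count from the examinations. The protocol ties some results explicitly to adverse-event recording: clinically significant laboratory values (6.2), IOP above 30 mmHg (9.3.13), and new abnormalities in vital signs, physical examination and ECG (13.4.6). I find no such link for fundoscopy findings. The photograph shell has a separate column for a reported adverse event, so finding and event are separate entries.

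A second objection concerns the remedy. The bleb is deliberate, and in primates re-attachment took 1-2 weeks (Protocol 4.11), while fundoscopy takes place at Day 1 and Week 1. A plain any-visit count could flag most patients for fluid or detachment. That is correct, and the fix allows for it.

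**Conclusion.** The point holds for the examination-based contrast and for cohort-level reporting. SAP 7.3 gives structural fundoscopy findings and fundus photographs no comparison except one that ignores 7 of 8 post-surgery fundoscopies in Cohorts 1-3a (6 of 7 in Cohorts 3b-5). Neither SAP Section 8 nor the final list provides the by-visit summary in Protocol 13.4.2 for these findings, subretinal fluid on OCT excepted. At cohort level a resolved event is counted only through adverse-event reporting.

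The 33% against 0% is an illustration for one patient in a cohort of three, not an estimate. The gap in the final tables closes to the extent that such events were reported as adverse events, which the documents do not allow one to judge. This should be corrected before the final outputs are produced. The study is descriptive, and no test or error rate is affected.

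**What to change.** In SAP 7.3, add a subsection for fundoscopy and fundus photography:

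- The contrast is a new or worsened finding, relative to the last examination before surgery, at any post-surgery visit through Week 48. Status at Week 48 is shown beside it. This baseline agrees with Protocol Section 6.
- Report n/N by finding, by eye where recorded, and by cohort.
- Show expected bleb-related subretinal fluid or detachment at the early post-operative visits in a separate row, with those visits fixed in the SAP, so that it does not swamp other findings.

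In the final output list, add one table and one listing (finding, eye, first and last visit seen), and the concomitant-medication listing from SAP 7.3.8. State whether the Section 9 profiles are final outputs. In SAP 7.4.4, confine the exploratory label to the three measures named there: photomontage, autofluorescence and microperimetry.

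The cost is SAP or memo wording and a little more programming on findings the protocol already has investigators record. Any-visit rates will look less favorable than Week 48 rates because early post-operative findings are counted; the separate bleb row and the Week 48 column let a reader see why.

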7.3.1 Adverse Events

AEs will be coded using MedDRA® (last version available at time of database lock). All reported events for all patients with cohort, event description, event date, resolution date, severity, outcome, relatedness, SAE indication, duration, High Level Term (HLT), System Organ Class (SOC), and Preferred Term (PT) will be listed. Specifically, AEs prior to treatment, treatment emergent adverse events (TEAEs), (i.e., started or increased in severity after the patient receives IMP, including abnormal lab results, ECG, etc.) and TEAEs of special interest will be listed separately. An overall summary table of TEAEs will also be provided that includes the number and percentage of TEAEs and patients with at least one TEAE in each dose cohort with:

- A fatal AE (death)
- At least one serious AE
- At least one severe AE
- At least one AE related to IMP
- At least one TEAE related to procedure
- Without any AEs

In addition, tables will present both the number and percentage of TEAEs and patients with TEAEs by SOC, HLT, PT, severity and cohort. Adverse events of special interest (AESI), detailed in the protocol, will be summarized by SOC, HLT, PT, severity and cohort. AESIs will be indicated, where appropriate in the patient profile listing of AEs. AEs related to the IMP and serious adverse events (SAEs) will be indicated in the AE listing and described in detail in the body of the report. Specific grouping will be done for events inflammatory in nature in the eye. Summary tables will be presented both with the inflammatory events grouped and without the events grouped. All events with the following preferred terms will be considered inflammatory in nature in the eye:

- Anterior chamber cell
- Anterior chamber inflammation
- Choroidal effusion
- Conjunctivitis
- Eye inflammation
- Eye discharge
- Keratitis

- Macular oedema
- Subretinal fluid
- Uveitis
- Vitreous floaters

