7.0 STATISTICAL ANALYSES

In this Phase I/IIa study, statistical analyses will be primarily descriptive and include patient-level reports referred to herein as patient profiles. Although UshStat is applied to only the study eye, where available, ophthalmic results for both the study and fellow eyes will be reported and clearly identified as “study” or “fellow.” Comparisons between the study and fellow eyes could be biased as the two eyes were not randomized to determine which eye received Investigational Product. The following sections describe data presentations which will be available for review prior to proceeding to each cohort and/or at the end of the study. Some variables (primarily ophthalmic variables) may be combined with others in patient profiles. Refer to [Sections 8](#) and [9](#) for sample reports.

Data will be summarized using graphical, tabular and/or listing presentations. In addition to patient profiles, continuous-scaled variables will be summarized by mean and standard deviation and/or median and range while categorical variables will be summarized in frequency tables. Percentages given in the summary tables will be rounded and therefore may not always add up to exactly 100 percent.

The primary analysis time point will be 48 weeks following administration of UshStat, but all results contributing to the primary and secondary endpoints and assessments of safety at all study visits will be presented.

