	PT2											
	All											

[Tables 3I](#) and [3J](#) list AEs prior to treatment and TEAEs by patient and cohort, respectively. [Table 3K](#) lists all adverse events of special interest (AESI).

Table 3I: Listing of Adverse Events Prior to Treatment by Patient and Cohort

Cohort	Patient ID	Enroll Date	AE Description	Event Date	Severity of Event	Outcome	Duration (Days)	MedDRA Classification		
								System Organ Class	High Level Term	Preferred Term
<hr/>										

Table 3J: Listing of TEAEs by Patient and Cohort

Cohort	Patient ID	Surgery Date	AE Description	Event Date	Outcome	Duration (Days)	Severity of Event	Relatedness		MedDRA Classification		
								Relation to Investigational Medicinal Product	Relation to Surgery	System Organ Class	High Level Term	Preferred Term
<hr/>												

Cohort	Patient ID	Surgery Date	AE Description	Event Date	Outcome	Duration (Days)	Severity of Event	Relatedness		MedDRA Classification		
								Relation to Investigational Medicinal Product	Relation to Surgery	System Organ Class	High Level Term	Preferred Term

Table 3K: Listing of Treatment Emergent Adverse Events of Special Interest by Patient and Cohort

Cohort	Patient ID	Surgery Date	AE Description	Event Date	Outcome	Duration (Days)	Severity of Event	Relatedness		MedDRA Classification		
								Relation to Investigational Medicinal Product	Relation to Surgery	System Organ Class	High Level Term	Preferred Term

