- [Table 3M](#): Mean Changes from Pre-surgical BCVA by Cohort and Visit
- [Table 3N](#): Mean Changes from Pre-surgical IOP by Cohort and Visit

- Table 3O: Patients Experiencing BCVA Change in the Study Eye at Week 48 Following Treatment by Cohort
- Table 3P: Patients Experiencing Elevated IOP in the Study Eye at Week 48 Following Treatment by Cohort
- **Tables 3Q-3S:** Changes in Ophthalmic Inflammation in the Study Eye by Cohort and Visit
- Figures 3T-3V: BCVA in Study and Fellow Eyes by Patient in Cohort X
- Figures 3W-3Y: IOP in Study and Fellow Eyes by Patient in Cohort X
- Figure 3Z: Mean Changes in BCVA in the Study Eye over Time by Cohort
- Figure 3AA: Mean Changes in IOP in the Study Eye over Time by Cohort
- **Listing 3BB:** Listing of Patients with Abnormal and/or Clinically Significant Labs
- Listing CC: Abnormal Physical Examination Listing by Patient
- **Table 3DD:** Mean Change in Continuous Laboratory Parameters by Cohort and Visit
- **Listing 3EE:** OCT Listing by Patient and Visit
- Figures 3FF-3HH: Central Retinal Thickness (OCT) for Study and Fellow Eyes in Cohort X
- Figures 3II-3KK: Macular Volume (OCT) for Study and Fellow Eyes in Cohort X
- Table 3LL: Change from Baseline in Vital Signs by Cohort and Visit
- **Listing 4A:** Static (GATE) Perimetry Data by Patient
- Figures 4B-4D: Volume of Full Field Hill of Vision Measured by Static (GATE) Perimetry by Patient in Cohort X
- Figures 4E-4G: 111pt grid-Volume of Full Field Hill of Vision Measured by Static (GATE) Perimetry by Patient in Cohort X
- **Listing 4H:** Kinetic (SKP) Perimetry Data by Patient
- Figures 4I-4K: SKP Data in Study Eyes by Patient in Cohort X
- **Listing 4L:** Full Field ERG Response (Study Eye) Amplitude and Implicit Time Data by Cohort, Patient and Visit
- **Table 4M:** Mean Peak Amplitudes and Latencies at Baseline (mfERG) by Cohort and Patient
- **Table 4N:** Central Field (Rings 1-3) Summary mfERG Data by Cohort and Patient
- **Table 4O:** Peripheral Field (Rings 4-6) Summary mfERG Data by Cohort and Patient
- Listing 5A: Detailed Listing of Immunologic Results from Blood Samples by Cohort and Patient
- Listing 5B: Biodistribution Endpoint Data

ADVERSE EVENT TABLE SHELL FOR TDU13600

PRIMARY SYSTEM ORGAN CLASS HLGT: High Level Group Term HLT: High Level Term Preferred Term n(%)	Cohort 1 (1.4×10^5 TU) (N=3)	Cohort 2 (4.7×10^5 TU) (N=3)	Cohort 3 (1.4×10^6 TU) (N=3)	All Cohorts (N=9)
Any Class	X (X%)	X (X%)	X (X%)	X (X%)
SOC1	X (X%)	X (X%)	X (X%)	X (X%)

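### The adverse event listings and tables have no study-eye/fellow-eye field, contrary to SAP 7.3, so ocular events of both eyes are pooled in the incidence counts

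*SAP*

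**What the plan says.** SAP 7.3 describes the primary endpoint as a set of safety components, "each of which will be presented at the patient and eye level", and points to Sections 8 and 9 for the layouts. AEs are excepted only in the sentence that follows, and only from the comparison of Day -28 with Week 48. SAP 7.0 sets the general rule that "ophthalmic results for both the study and fellow eyes will be reported and clearly identified" by eye.

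For AEs, SAP 7.3.1 names the listing fields: "All reported events for all patients with cohort, event description, event date, resolution date, severity, outcome, relatedness, SAE indication, duration", followed by the three MedDRA levels. An event is treatment-emergent if it "started or increased in severity after the patient receives IMP". For inflammation, "Specific grouping will be done for events inflammatory in nature in the eye", and membership of the group is fixed by a list of eleven preferred terms.

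The layouts are in SAP 8.3.1 (for example "Table 3J: Listing of TEAEs by Patient and Cohort") and in the patient profiles of Section 9. The memo of 30 August 2019 replaces the AE table format with the "ADVERSE EVENT TABLE SHELL FOR TDU13600", which counts patients by MedDRA level and cohort, with 3 patients per cohort and 9 overall.

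**The concern.** AE incidence is the first primary endpoint. The product goes into one eye, and protocol 4.10 names the other eye as the within-patient control. The treatment-emergent definition is a rule about the patient and about time since dosing. It sets no condition on the eye, so an event in the uninjected eye qualifies.

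Such events are plausible. Exclusion criterion 1 (protocol 8.2, SAP 4.2) bars glaucoma, significant lens opacity and pre-existing uveitis in the study eye only, so a fellow eye may enter with any of these, and worsening would count. The inflammatory group also contains terms that are not specific to an operated eye, such as conjunctivitis, macular oedema and vitreous floaters.

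Inflammation is the central safety question. It is the listed stopping criterion (protocol 8.4), it heads the dose-limiting toxicities (protocol 8.5), and uveitis cases prompted the steroid schedule in Amendment 8. A grouped inflammatory count that cannot say which eye was affected is hard to read as evidence about the injected eye.

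**Working it through.** The plan states no figure on this point, so there is none to reproduce. The check is a comparison of the places where AEs are shown, then a short illustration.

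**Step 1. Look for an eye field wherever AEs are shown.**

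| Place | Content | Eye field |
|---|---|---|
| SAP 7.3.1, listing fields | cohort, description, dates, severity, outcome, relatedness, seriousness, duration, MedDRA levels | none |
| SAP 8.3.1, Tables 3A-3H | counts by event type or MedDRA level, severity and cohort; 3E and 3F group inflammatory events; 3G and 3H cover relation to product and to procedure | none |
| SAP 8.3.1, Tables 3I-3K | AE listings; each has a free-text description column | none |
| SAP Section 9, profile AE table | description, dates, outcome, severity, special-interest and serious flags, relation to surgery and product, MedDRA terms | none |
| 2019 memo, Tables 3A-3G and AE shell | patients by four MedDRA levels and cohort | none |
| 2019 memo, listings 3H-3K | titles by patient and cohort; no new layout given | none |
| SAP Section 9, OCT and fundus-photo profile tables | a Reported AE flag with study and fellow sub-columns (the OCT table is partly broken in extraction) | yes |

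The last row is the only by-eye AE information. It flags AEs noted at those two assessments and does not feed the incidence counts. The OCT listing in SAP 8.3.4 has no such flag, and the memo's list of all final outputs names neither the patient profiles nor a fundus-photo listing.

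**Step 2. Compare with the other ocular primary components.** Visual acuity, inflammation grades, intraocular pressure and OCT (SAP 7.3.2-7.3.5, Tables 3L-3N and 3U) have study-eye and fellow-eye columns. The memo even divides ocular history into a study-eye listing (2D) and a fellow-eye listing (2E). Among the ocular primary results with dedicated listings, AEs are the exception.

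**Step 3. What pooling does to a count.** For any row of a patient-based table, let S be the patients with the event in the study eye, F those with it in the fellow eye, and B those with it in both.

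- Pooled count = S + F - B.
- Excess over the study-eye count = F - B.

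Only patients whose event in that row is confined to the fellow eye change the count. Take one such patient: S = 0, F = 1, B = 0, so the pooled count is 0 + 1 - 0 = 1.

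Exact (Clopper-Pearson) 95% intervals at the memo's sample sizes use these limits. For 0/n the upper limit is 1 - 0.025^(1/n). For 1/n the lower limit is 1 - 0.975^(1/n) and the upper limit is the 97.5% quantile of a beta(2, n - 1) distribution.

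| | Study eye only | Pooled |
|---|---|---|
| One cohort, n = 3 | 0/3 = 0% (0 to 70.8) | 1/3 = 33.3% (0.8 to 90.6) |
| All cohorts, n = 9 | 0/9 = 0% (0 to 33.6) | 1/9 = 11.1% (0.3 to 48.2) |

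The intervals overlap widely, as they must at these sizes. In a descriptive study the count itself is what is read, and it moves from none to one.

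**The case against.** The strongest reply is that the study is descriptive and small, every event is listed by patient, and the reader can work out the eye. The listings carry a free-text description that may name it. Product-related and procedure-related events are tabulated separately, and protocol 11.2 treats an event as unrelated when a typical disease event is clearly the more likely cause. Related and serious events are also to be described in the report text. The by-eye sentence in SAP 7.3 covers laboratory values and vital signs too, so it must mean by eye where that applies.

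Much of this stands as a limit on the point, but it does not remove it. Where applicable plainly includes ocular AEs. A description may give the eye but is not required to, and free text cannot drive a table. Relatedness is an investigator's judgement in an open-label study and does not replace laterality, although it does mean that a fellow-eye event judged unrelated stays out of the related-event tables.

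A reader might infer three stronger things that the documents do not support:

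- That no shell records the eye of an AE. The OCT and fundus-photo profile tables do.
- That fellow-eye events are attributed to the injected eye. The counts are at patient level, and nothing assigns them to an eye; the two eyes are pooled.
- That the fellow-eye control is lost for the whole primary endpoint. The other ocular components are shown by eye. The contralateral comparison is written into the secondary endpoints (protocol 6.2, SAP 5.2), and SAP 7.0 warns that it may be biased because the eyes were not randomised.

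The remark in the amendment history that macular edema is common in this disease also carries limited weight: existing edema that does not worsen is not treatment-emergent.

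**Conclusion.** The point holds as a reporting gap. SAP 7.3 promises AE results by eye, and none of the AE listings, AE summary tables or the 2019 AE shell delivers them. Followed as written, the plan pools ocular events of the injected and uninjected eyes in the first primary endpoint, including the grouped inflammatory count.

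The real size is unknown. The documents give no rate of fellow-eye-only events, so a probability that a cohort is affected would rest on a guess. The supportable statement is the illustration: one such patient turns 0/3 into 1/3, or 0/9 into 1/9, in the row concerned. It assumes that the patient has no study-eye event in the same row; otherwise that row's count is unchanged.

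The case report form is not among the documents, so no conclusion is possible on whether laterality is collected. The gap shown is in what is reported. Correcting it is a cheap improvement to the main safety table; the gap does not invalidate the endpoint.

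**What to change.** - Add one column, with values study eye, fellow eye, both, or non-ocular, to memo listings 3H-3K and to the patient-profile AE table.
- Split the ocular rows of memo Tables 3A-3G by eye.
- In the inflammatory table (memo Table 3E), show the study-eye count with the fellow-eye count beside it.
- Add the affected eye to the field list in SAP 7.3.1, so that text and shells agree with SAP 7.3.
- State that any study-versus-fellow reading of AE counts is descriptive, in line with the caution in SAP 7.0.

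The cost is a revision of the shells and their programs. If the case report form does not record laterality, it has to be derived from the AE description or the eye examination records, with queries to sites where these are unclear. No new patient assessments are needed.
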